1.4 Description of Interventions to be tested

Decision aids can be delivered within or prior to specialty visits using a variety of modes, including paper, tablet, and computer-based platforms. Decision aids delivered prior to the clinical visit prepare patients for decisions by providing information to have a basic understanding of facts discussed in a clinical consultation. Members of our team [REDACTED] have extensive

experience testing decision aids outside of the clinical visit. Most of the decision aid literature tests them prior to provider visits; these trials improve knowledge, but do not necessarily improve patient-provider communication.^{44,45,53-55} The Mayo Clinic team typically tests decision aids for use with the clinical visit. These tools are minimal detail props to promote a better conversation. Several clinical trials of decision aids delivered within visits show improvement in patient knowledge comparable to tools delivered prior to consultation.^{56,57} In contrast to tools delivered prior to the visit, tools delivered within a visit may promote better patient involvement in decision making. How the two forms of decision aid delivery might combine to improve outcomes is also uncertain. Despite the promise of decision aids, they are rarely used in specialty practice for prostate cancer and in-visit decision aids have never been tested as a tool to mitigate both disparities in knowledge as well as in functional outcomes for prostate cancer.

Whether in-visit and out-of-visit decision aids potentiate each other in enhancing decisional quality is an additional important unaddressed question that could inform eventual larger scale health services implementation strategies in underserved patient populations with PCa.

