12.2.2 Sample Size and Power Considerations

Sample size and power calculation: We first consider power and sample size under the assumption that patients within the same site are uncorrelated. As this is unlikely to be the case in a group randomized trial, we will discuss the adjustment of the sample size estimate to account for this correlation between patients in the next subsection. A recent Cochrane review suggests that most patients can accurately answer 50% (standard deviation of 12%) of the questions asked of them.⁷⁰ On average, DAs increase that knowledge by 20% to 60% of questions asked being answered correctly, but 95% of trials show absolute knowledge increases of 10% or greater. We will consider an absolute 8% increase in knowledge as a clinically meaningful effect size for either during-consultation Prostate Choice or pre-consultation DA in this clinical trial. Note that the four arms of this study make up a 2 X 2 factorial design. Thus, it is natural to consider evaluating the decision aids using a two-way analysis of variance (ANOVA). In this case, the two factors in the ANOVA will be having received during-consultation Prostate Choice (yes or no) and having received pre-consultation DA (yes or no). We will consider simultaneously testing (at a significance level of 0.025 for each test) the main effects of the two decision aids as our primary analysis. That is, we will simultaneously test the null hypothesis that the average knowledge (i.e. the proportion of correct responses to questions) among those who received the pre-consultation DA is equal to that among those who did not (vs. an alternative that these two averages are not equal), and the null hypothesis that the average knowledge among those who received the during-consultation Prostate Choice is equal to that among those who did not (vs. an alternative that these two averages are not equal). A total sample of 100 patients (25 patients per arm) would give us approximately 85% power to detect a difference between those receiving pre-consultation DA and those not receiving pre-consultation DA, under the alternative that the average knowledge among those receiving pre-consultation DA is 58%, and that the average knowledge among those not receiving pre-consultation DA is 50%, using a two-sample t-test (with two-sided alternative) with a 2.5% significance level (this is equivalent to the F test for the main effects in the ANOVA). Under a similar alternative, the same can be said for the during-consultation Prostate Choice decision aid. Thus, if patients within each site were not correlated with each other, our target sample size would be 100 patients. There will be some, but insufficient power to detect an interaction between the two decision aids, but such effects are rare and not anticipated in this study. Therefore, we will not test for such an interaction in the primary analysis.

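### Section 12.2.2 uses 50% both for unaided men and for control groups half of whom get the other aid, does not link overlap between the aids to power, and no planned knowledge analysis compares one aid alone with usual care

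*Combined protocol and SAP*

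**What the plan says.** Section 12.2.2 opens its sizing with this: "A recent Cochrane review suggests that most patients can accurately answer 50% (standard deviation of 12%) of the questions asked of them". It then sets the target: "We will consider an absolute 8% increase in knowledge as a clinically meaningful effect size for either during-consultation Prostate Choice or pre-consultation DA". The primary analysis consists of "simultaneously testing (at a significance level of 0.025 for each test) the main effects of the two decision aids as our primary analysis". For the pre-consultation aid the alternative is that "the average knowledge among those receiving pre-consultation DA is 58%, and that the average knowledge among those not receiving pre-consultation DA is 50" per cent. For the other aid: "Under a similar alternative, the same can be said for the during-consultation Prostate Choice decision aid". The stated power is about 85% with 100 uncorrelated patients.

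On interaction, the same section says that power to detect one is insufficient but that "such effects are rare and not anticipated in this study", and it leaves the interaction out of the primary analysis. Section 1.4 reads differently: "How the two forms of decision aid delivery might combine to improve outcomes is also uncertain".

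The model in section 12.2.1 has one fixed effect per aid and a random site intercept. Section 12.4.2 reuses that structure for the secondary endpoints. Section 1.2 gives as an aim testing the aids singly and together on knowledge, among other outcomes, and section 1.3 describes the design as looking at their separate and added effects. Objectives 2.2.1 to 2.2.3 compare each aid alone, and the pair, with usual care, but only for quality of life and treatment utilization.

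**The concern.** The 50% has two meanings. It is what men score before any gain from an aid, which here describes the usual-care arm. It is also the mean of everyone not receiving a given aid. With equal arms, half of that second group receives the other aid, so the two meanings agree only if the other aid does nothing on its own.

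The label matters less than what it hides. A main effect averages an aid's gain over usual care with its gain on top of the other aid. Both tests score the same 12 items, and section 1.4 treats the behaviour of the combination as unknown. If the aids overlap, both primary contrasts shrink together. Two aids that each deliver the 8 points the plan calls meaningful could then both miss significance, and no knowledge analysis is prespecified that would show why.

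**Working it through.** **Inputs.** From section 12.2.2: unaided mean 50%, SD 12 points, 8-point effect for either aid, two-sided 0.025 per test, 100 patients (50 against 50 for each main effect). Equal arms are confirmed in section 12.3.1. Arm letters follow section 8.0: A both aids, B pre-consultation only, C during-consultation only, D usual care. Section 1.5 swaps B and C, which does not affect the results.

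**1. The plan's figure.** Noncentrality = 8 / (12 × √(2/50)) = 8 / 2.4 = 3.33. The noncentral t with 98 df gives 85.3% (also 85.3% with 97 df for the two-factor ANOVA); the normal approximation gives 86.3%. The stated 85% reproduces.

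**2. What the 50% implies.** The main effects are:

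- pre-consultation aid: (A + B)/2 − (C + D)/2
- Prostate Choice: (A + C)/2 − (B + D)/2

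Take 58 against 50 on both margins.

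- With no interaction (A − B − C + D = 0), the arms are A = 62, B = C = 54, D = 46. Usual care is then 46%, not 50%.
- With D held at 50, the arms are A = 66, B = C = D = 50. Neither aid then works alone.

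Taking instead D = 50, B = C = 58 and no interaction gives A = 66. The margins are (66 + 58)/2 = 62 and (58 + 50)/2 = 54. The difference is still 8, so power is still 85.3% and N is unchanged.

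**3. What two 8-point main effects require.** Adding the two main effects gives A − D. If both are 8, A − D = 16 whatever B and C are, so A = 66% when D = 50%.

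**4. Less-than-additive effects.** With B = C, each main effect is (A − D)/2. Assume D = 50 and B = C = 58, with 100 independent patients:

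| Combined arm | Main effect | Power per test |
|---|---|---|
| 66% | 8 points | 85% |
| 64% | 7 points | 74% |
| 62% | 6 points | 59% |
| 58% | 4 points | 28% |

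The cluster-adjusted totals in section 12.2.2's own table are 140 patients for 8 points, 252 for 6 and 504 for 4.

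**5. After clustering.** With 172 patients over 20 sites, m = 8.6. The design effect is 1 + 7.6 × 0.1 = 1.76 and the effective N is 172/1.76 = 97.7, so the powers above barely change.

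**6. Precision of the missing contrasts**, at effective N 97.7:

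- main effect: SE = 12 × √(4/97.7) ≈ 2.4 points
- one arm against usual care: SE = 12 × √(8/97.7) ≈ 3.4 points

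**The case against.** The strongest reply is that the sizing is sound. Power depends on the difference and the SD, not on the 50% level. Section 12.2.2 names the contrast it powers, recipients of an aid against non-recipients, as the ANOVA main effect. It also declares the no-interaction assumption, and its table already covers 4- and 6-point effects. All of that stands.

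A reader might infer three stronger things that the documents do not support.

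- **That the 85% is wrong or the trial too small because of the mislabelled control mean.** It is not; step 2 shows the same power at 62 against 54.
- **That the 85% holds only under full additivity.** Section 12.2.2 reports gains of 10 points or more in 95% of trials. With each aid alone at 60%, a combined arm at 66% is 4 points below the additive 70%, and both main effects are still 8.
- **That each test by itself needs 66% in the combined arm.** If Prostate Choice did nothing (A = B = 58, C = D = 50), the pre-consultation test would still have an 8-point effect.

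It is also fair to say that section 1.4 speaks of outcomes and of the aids strengthening each other, which would raise the main effects. The tools differ in style, and no figure for overlap appears anywhere. Overlap is therefore a possibility to plan for, not a documented expectation. Nor does any section say that a null main effect would be reported as an aid not working.

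The reply leaves a gap. The plan never connects overlap to the smaller-effect rows of its table, and it has no knowledge analysis that would reveal overlap.

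**Conclusion.** The point holds in a limited form. The 50% cannot be both the usual-care mean and the mean of each control margin if each aid works alone. This is a wording fault with no effect on the 85% or on N. Two 8-point main effects put the combined arm 16 points above usual care, which the plan does not state. Its confidence about interaction in section 12.2.2 sits uneasily with section 1.4.

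The fall in power per test from 85% to 74%, 59% or 28% rests on usual care at 50%, each aid alone at exactly 58% and SD 12. Larger single-aid gains leave margin.

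The more useful finding concerns analysis. Section 1.2 sets out to learn what each aid does for knowledge by itself and with the other, while the main-effects model and the objectives provide no such comparison for knowledge. This should be corrected, but it does not threaten the primary tests.

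**What to change.** **Section 12.2.2.** State the four assumed arm means, for example usual care 50%, each aid alone 58%, combined 66%, with margins 62% and 54%. Say that the 85% refers to an 8-point main effect. Note that overlap between the aids would move the trial towards the 6- and 4-point rows of the existing table.

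**Sections 12.2.1 and 12.4.2.** Keep the two main-effect tests as primary, unchanged. Prespecify as supportive analyses, from the same random-site-intercept model with an interaction term added:

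- the four knowledge arm means;
- the contrasts of each aid alone, and of the combination, with usual care, all with confidence intervals.

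State that a null main effect will be interpreted alongside these.

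**Cost.** Text and one table from data already collected; no extra patients and no change to alpha or the primary tests. The supportive contrasts are less precise (SE about 3.4 points against 2.4 for a main effect, at 172 patients and ICC 0.1) and are not powered, which the plan should say.

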
Sample size adjustment due to cluster randomization: As mentioned above, we do not believe that subjects within each site will truly be independent of each other. Thus, the application of the standard sample size calculation, as above, may lead to an underpowered study. Since we expect $k=20$ sites to participate in this clinical trial, we would need about $m = 5$ patients to be enrolled from each site (on average) to achieve a total enrollment of 100 patients. Assuming the intra-site correlation coefficient ρ will be approximately 0.1 (rather than zero) for all study sites, we must inflate the target sample size by a factor⁷¹ of $1+(m-1)\rho=1+(5-1)*0.1=1.4$ to achieve comparable power to that in a patient-level randomized trial. This comes about as follows (we consider the pre-decision DA here, but the same derivation holds for the during-consultation Prostate Choice). Suppose the variance of knowledge (Y) is the same for all patients, and is equal to σ^2 , and that n is our total sample size, with $n/2$ patients receiving the pre-consultation DA and $n/2$ not receiving the pre-consultation DA. Assuming no correlation between patients within the same site, the variance of the sample mean of knowledge among those receiving pre-consultation DA (\bar{Y}_1) will be $\sigma^2/(n/2)$, as will that for the sample mean of knowledge among those not receiving pre-consultation DA (\bar{Y}_2), and our test statistic would have the form $[(\bar{Y}_1 - \bar{Y}_2) - (\mu_1 - \mu_2)]/[\sigma^2/(n/2) + \sigma^2/(n/2)]^{(1/2)}$ (note that the denominator of this statistic simplifies to $[4\sigma^2/n]^{(1/2)}$). However, this is not a correct assumption in our case. In particular, suppose that we have 20 sites, and within each site, we have m (5) patients, between each of whom the

correlation is ρ (0.1) (meaning the covariance between any two patients in the same site is $\rho\sigma^2$). In this case, the variances of the sample means are not $\sigma^2/(n/2)$, but rather:

$$\begin{aligned}
 Var(Y_1) &= Var(Y_2) = Var\left(\frac{1}{\binom{n}{2}} \sum Y_i\right) \\
 &= \frac{1}{\binom{n}{2}^2} \left[\binom{n}{2} \sigma^2 + (2) \binom{\binom{n}{2}}{m} \left(\frac{m!}{(m-2)! 2!} \right) \rho \sigma^2 \right] \\
 &= \frac{1}{\binom{n}{2}} \left[\sigma^2 + \left(\frac{1}{m} \right) m(m-1) \rho \sigma^2 \right] \\
 &= \frac{1}{\binom{n}{2}} [\sigma^2 + (m-1)\rho\sigma^2] \\
 &= \frac{\sigma^2}{\binom{n}{2}} [1 + (m-1)\rho].
 \end{aligned}$$

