Thus, the denominator of our test statistic should actually be $[(4\sigma^2/n)(1 + (m-1)\rho)]^{(1/2)}$. Therefore, if we replace the original sample size ($n=100$) with $n(1 + (m-1)\rho) = 100*1.4 = 140$ in the denominator of our original test statistic, we will have a test statistic which accounts for the correlation of 0.1 between subjects within each of the 20 sites. Hence, we will target an effective sample size of 140 patients (approximately 35 patients per arm, 7 patients per site). The total sample size may be further inflated by 20% to account for ineligible, cancel and loss to follow-up for longer term secondary outcomes and allow increased power to detect racial/ethnic differences. Therefore, a total number of 172 patients will be enrolled into this clinical trial. These 172 patients, recruited from 20 participating sites (about 9 patients per site) will receive the intervention (or control) to which their location is randomized.

Though we have chosen to power this study based on an absolute meaningful difference of 8%, we determined the necessary sample size for a range of meaningful differences. In each case, the target power was approximately 85% (thought it varied slightly, as we only considered sizes which were divisible by 20, given the number of expected sites) with joint main effect two-sided t-tests with two-sided alternatives at the 2.5% significance level. These sample sizes are as follows (not adjusted for ineligibility, cancel and loss to follow-up):

Meaningful Difference	Total sample size without correlation within sites	Total sample size adjusted for correlation within sites
4%	360	504
6%	180	252
8%	100	140
10%	60	84
12%	40	56

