12.3 Sample Size, Accrual Time, and Study Duration

12.3.1 Patient Population: In order to achieve higher minority accrual (at least 43 AA, and at least 43 AI/AN, and up to 86 White, and/or Asian), we will impose a restriction of at most 50% White and/or Asian participants at each site. Patient accrual will be restricted to AA and AI/AN minority once 50% White or Asian patients are enrolled. We are not oversampling Asian men (n=4) because there are no known disparities in this population. As patient recruitment is not blinded to site in the cluster randomization, we will encourage sites to identify patients prior to randomization and conduct recruitment by an individual independent from the one who delivers the intervention to reduce bias. We will recruit 172 patients (43 per arm).

In addition, in order to prevent imbalance between the arms, sites that over-accrue to the study may be asked to close the study at their institution. Finally, institutions will be given a recruitment goal of at least 2 men who report Hispanic/Latino ethnicity per site, and will be required to hold two slots for Hispanic/Latino participants for the first year of the study in hopes of accruing a similar number of Hispanic/Latino men. These slots will be released after the first year of the study if no Hispanic/Latino participants have been recruited at a given site.

12.3.2 Accrual Rate and Accrual Duration: Based on an estimated accrual rate of 10 patients per month across the 20 participating practices, we expect 1 year to identify and train participating practices, approximately 18 months to enroll patients into the clinical trial and another 18 months to collect follow-up outcomes and perform data cleaning and statistical analysis. The study duration of this clinical trial will be 4 years.

12.3.3 Primary Endpoint Completion Date for ClinicalTrials.gov Reporting: For purposes of ClinicalTrial.gov reporting, the Primary Endpoint Completion Date (PECD) for this study is the time the last patient registered has been followed for at least 12 months.

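### Section 12.2.2 takes the design effect at 5 patients per site but plans 7, so 140 patients give about 80% power, not about 85%, and the 4% and 6% table rows fall far short

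*Combined protocol and SAP*

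**What the plan says.** Section 12.2.2 starts from independent patients. For an 8% difference (58% against 50%, SD 12%) and a two-sided 2.5% t-test for each main effect, it says: "A total sample of 100 patients (25 patients per arm) would give us approximately 85% power to detect a difference".

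It then allows for clustering. With 20 sites expected, "we would need about $m = 5$ patients to be enrolled from each site (on average) to achieve a total enrollment of 100 patients", and an assumed intra-site correlation of 0.1 gives a factor of 1 + (5 − 1) × 0.1 = 1.4. The conclusion is: "Hence, we will target an effective sample size of 140 patients (approximately 35 patients per arm, 7 patients per site").

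A further addition follows: "The total sample size may be further inflated by 20% to account for ineligible, cancel and loss to follow-up for longer term secondary outcomes", and also to add power for racial/ethnic differences. Enrolment becomes 172: "These 172 patients, recruited from 20 participating sites (about 9 patients per site").

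A table then lists sample sizes for differences of 4% to 12%. The text says of all rows: "In each case, the target power was approximately 85" per cent, although "it varied slightly, as we only considered sizes which were divisible by 20, given the number of expected sites". The cluster-adjusted column is the unadjusted column times 1.4 in every row.

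**The concern.** The design effect depends on how many patients each site contributes to the trial that is actually run. Section 12.2.2 evaluates it at the cluster size of the uninflated trial (100/20 = 5). It then adds patients to the same 20 sites and does not recompute it, although the sentence giving the 140 also gives the new cluster size of 7. Adding patients to a fixed number of sites buys less information per patient, so a fixed factor overstates power, and the overstatement grows with the sample size.

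Two things are at stake. A team that takes 140 evaluable patients to be enough would regard the other 32 of the 172 as reserve, when the stated power depends on them. And a reader of the table would believe that 20 sites could detect a 4% or 6% difference with about 85% power by enrolling 504 or 252 patients.

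**Working it through.** **Inputs** (all from Section 12.2.2): SD 12%; two-sided alpha 0.025 per main effect; 20 sites; intra-site correlation 0.1; half of the patients on each side of a main effect. Equal site sizes are assumed, as in the plan's derivation.

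**Formulas.** Design effect DE = 1 + (n/20 − 1) × 0.1. Effective size n_eff = n/DE. Noncentrality λ = (difference/12) × √(n_eff/4). Power comes from the noncentral t distribution with n − 2 df. The last column of the table below uses 17 df instead: 20 sites less the three fixed coefficients (intercept and two decision aids) of the Section 12.2.1 model, because both decision aids are assigned by site.

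**The plan's figures reproduced.** For n = 100 with DE = 1, λ = (8/12) × √25 = 3.33 and power is 85.3%, as stated. The other unadjusted rows give 81.9% (360 for 4%), 86.2% (180 for 6%), 82.0% (60 for 10%) and 79.3% (40 for 12%). The product 100 × 1.4 = 140 is also correct, but 1.4 fits 140 patients only in 28 sites of 5, where power is 85.6%.

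**At the planned cluster size.** For n = 140, DE = 1 + 6 × 0.1 = 1.6, n_eff = 140/1.6 = 87.5, λ = (8/12) × √21.875 = 3.12, and power is 80.2%. Taking df from the effective size gives 79.7%, and the normal approximation gives 81.0%.

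| Difference | n in 20 sites | Per site | DE | n_eff | Power, n − 2 df | Power, 17 df |
|---|---|---|---|---|---|---|
| 4% | 504 (printed) | 25.2 | 3.42 | 147.4 | 41% | 36% |
| 6% | 252 (printed) | 12.6 | 2.16 | 116.7 | 67% | 60% |
| 8% | 140 (printed) | 7.0 | 1.60 | 87.5 | 80% | 74% |
| 8% | 160 | 8.0 | 1.70 | 94.1 | 83% | 77% |
| 8% | 172 (enrolment) | 8.6 | 1.76 | 97.7 | 85% | 79% |
| 10% | 84 (printed) | 4.2 | 1.32 | 63.6 | 85% | 80% |
| 12% | 56 (printed) | 2.8 | 1.18 | 47.5 | 87% | 83% |

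**What 85% requires in 20 sites (n − 2 df).** For 8%, 174 patients (172 gives 84.8%, 174 gives 85.1%). That is 174 − 140 = 34 more than 140, against the 172 − 140 = 32 that the plan adds. For 10%, 85 patients; for 12%, 53. For 6%, about 1,120 (1,000 gives 84.4%, 1,400 gives 86.1%). For 4% there is no solution: n_eff = n/(0.9 + 0.005n) cannot exceed 20/0.1 = 200, where power is about 55%.

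**The case against.** The strongest reply is that the trial enrols 172, not 140. The knowledge questionnaire is completed at the consultation visit (Section 12.2), so loss by 12 months does not remove primary outcomes; only ineligible, cancelled or incomplete cases do. All 172 evaluable give 84.8%, and 160 give 83%. This stands. A reader might infer that the planned enrolment is too small, but the documents do not support that on the plan's own assumptions.

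A second reply is that the inputs are loose. The plan's unadjusted rows themselves run from 79% to 86%, so 80% lies within its own scatter. An intra-site correlation of 0.07 would restore 85% at 140, and 24 sites would give 83%. This limits the weight of the 8% row. It does not rescue the statement, because the plan fixes 0.1 and 20 sites and claims to match the 85% of 100 independent patients. It does nothing for 41% and 67%. Nor does calling 140 an effective sample size help, since the same sentence counts it as 35 patients per arm and 7 per site.

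Third, the 20% was never purely a reserve for the primary endpoint: it names loss for longer-term outcomes and racial/ethnic power as well. That is correct. The point is only that none of the named purposes is restoring the design effect, which is where the patients go.

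Two further inferences are tempting and unsupported:

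- Section 12.3.1 says that "sites that over-accrue to the study may be asked to close the study at their institution". A reader might take this as a forecast of unequal sites. Its stated aim is to limit imbalance between arms, and the documents give no spread of site sizes. Unequal sizes would lower power, but by an amount that cannot be taken from the plan.
- The 78% power for minority men in Section 12.4.2 might seem to carry the same error. The number of patients behind it is not given. On the natural reading, 80% of 172 is about 138, which gives about 80% at its own cluster size, slightly above the figure stated. No error is shown there.

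**Conclusion.** The plan is wrong as written in Section 12.2.2. On its own formula and inputs, 140 evaluable patients in 20 equal sites give about 80% power for an 8% difference, about 5 points below the stated figure. The 4% and 6% rows give about 41% and 67%, and 85% for 4% cannot be reached with 20 sites at any enrolment. The 10% and 12% rows use the same wrong factor but remain adequate.

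The consequence for the trial itself is modest: 172 evaluable patients restore about 85%, with essentially none to spare. These figures assume patient-level df. Section 12.2.1 names no df method, so neither set in the table can be called the plan's own. On 17 between-site df the powers are about 74% at 140 and 79% at 172.

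**What to change.** In Section 12.2.2:

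1. Compute the design effect at the planned cluster size: 1.6 at 140 patients and 1.76 at 172.
2. Restate power with its assumptions, for example: with 20 sites of equal size, intra-site correlation 0.1, SD 12% and a two-sided 2.5% t-test on patient-level df, 140 evaluable patients give about 80% power and 172 give about 85%; unequal site sizes or between-site df lower these figures.
3. Say that essentially all of the addition from 140 to 172 is needed to reach about 85% for the primary comparison.
4. Recompute the third table column on one stated basis. For 85% power in 20 equal sites with patient-level df: 4% not attainable; 6% about 1,100 or more, not practical; 8% about 175; 10% about 85; 12% about 53 to 55. Because the second column is only roughly 85%, the two columns will not correspond row by row, and a note should say so. To match each unadjusted size n0 instead, use n = 0.9 × n0/(1 − 0.005 × n0), which gives about 1,620, 180, 77 and 45 for 6% to 12%, and no solution for 4%.

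The cost is a few sentences and one table column. The 172 patients and 20 sites can stay. The price is a less favourable stated power at 140 and an open statement that there is little spare capacity for lost primary outcomes.
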